Aim 3. Examine the feasibility and acceptability of the internet-delivered mindfulness-based intervention (iMBI), called “Mindfulness-based Queer Resilience (MBQR)”, for HIV prevention. We will enroll and randomize a sample of 60 distressed, high-risk YMSM into one of two groups: MBQR intervention ($n=30$) or active control condition ($n=30$). We will aim to over enroll YMSM of color (e.g., Black/Latinx YMSM) and anticipate the group to include **approximately 50-60% Black/Latinx YMSM (or YMSM of color)**. Primary outcomes are **HIV and STI testing** and self-reported sexual risk behaviors. Secondary outcomes are stress biomarker (fingernail cortisol levels), psychological health, minority stress and coping. The study will examine recruitment and retention, number of sessions attended, self-reported at-home practice of mindfulness, completion of assessment, and acceptability of the intervention.

2. Aim 3 Study Design Overview

[figure not shown]
The methodological approach includes a 2-arm trial of MBQR vs. a *health education* control group, with up to $n=30$ per arm (total Aim 3 sample size = up to 60 participants enrolled and randomized). The study is intended to evaluate the impacts of MBQR on the outcomes outlined in the Specific Aims above.

All research assessments will take place digitally using Qualtrics, LLC (Provo, UT, USA) survey management tool. Participants will be sent secure links via email and SMS that can be accessed with their participant identification number. The MBQR intervention classes will be offered online via Zoom by a trained and qualified mindfulness instructor.

Baseline assessment links will be sent to all enrolled participants and completed prior to the start of the interventions. Follow up assessments will be conducted at three time points (post-intervention, 6-months follow up, and at 1-year follow up (for intervention participants only)).

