MBQR-hybrid is an online-based mindfulness course asynchronously facilitated by queer mindfulness teachers, with weekly home practice and additional reflection and reading activities that can be completed by participants independently via study website portal. Participants will also have the option of participating in weekly live 1-hour sessions. MBQR-hybrid is designed to be completed within a 3-months time frame (10 modules that can be paced to complete in a 10-14 weeks time frame).

6. Other Study Details:

Compensation

Participants will have the opportunity to earn up to \$340 (intervention group) and up to \$300 (control group) for their time and effort in this study. Participants will only be compensated for the study components that they choose to complete. Partial

compensation will not be provided. If a participant withdraws from the study early, they will not be compensated for the study components that are incomplete.

Below is an outline of the compensation structure by study element.

T1: Baseline (\$40 Total)

\$20 - HIV testing**

\$20 - Cortisol nail sample

Intervention / Control (\$50 Total)

\$50 - \$5 per assessment x 10

T2: Post-Intervention (\$70 - 110 Total)

\$20 - STI/HIV testing

\$20 - Cortisol nail sample

\$30 - Assessment

\$40 - Exit Interview*

T3: 6-Month Follow Up (\$70 Total)

\$20 - STI/HIV testing

\$20 - Cortisol nail sample

\$30 - Assessment

T4: 1-year* Follow Up (\$70 Total)

\$20 - STI/HIV testing

\$20 - Cortisol nail sample

\$30 - Assessment

*MBQR Intervention Group Only; Control group will be invited to take part in a MBQR-hybrid course after their 6-month follow up is complete. This additional course is optional. Control group members who opt to take MBQR-hybrid will be invited to complete a post-intervention assessment and exit interview (\$30 and \$40 each).

**Compensation for HIV testing is not limited to the self-testing kit provided by the study.

Total Possible Compensation for Control Participants = \$300

Total Possible Compensation for Intervention Participants = \$340

Withdrawal during intervention

We anticipate some amount of dropout during the study. If a participant in MBQR decides to withdraw from the study during the course or if a control participant discontinues the health education training, they will still be invited to take part in the follow up assessments.

Confidentiality

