Data management will be performed by downloading data routinely during active data collection periods, and assessing data for missingness and errors. Data will be maintained in password-protected Microsoft Excel Spreadsheets, and then exported using .csv or SPSS functions for data analysis.

Quality Assurance

Provider Training: MBQR delivery will be performed by (a) qualified or certified MBSR instructor(s), or (b) PhD-level psychologists/licensed mental health professionals with more than 400+ clinical hours as well as extensive experience in working with LGBTQ+ populations and/or mindfulness⁴⁹. MBQR instructor training involves a 20-30 hour intensive training that covers the principles of MBQR, specific teaching content, diversity-related issues, group dynamics, and inquiries. Training will take the format of presentations, group discussion, role-play, and feedback from PI and peers. Training will be delivered by PI [name].

MBSR teacher certification is fairly extensive, and accreditation occurs through qualified schools / centers for mindfulness. Examples of criteria for becoming a certified MBSR teaching include (i) completion of an eight-week MBSR course as a participant, (ii) completion of several

multi-day residential training courses in mindfulness based stress reduction practice and teaching, (iii) substantial experience in teaching MBSR, (iv) strong references letters from colleagues and participants who have taken your MBSR courses, (v) completion of several multi-day mindfulness meditation retreats, (vi) have a graduate degree in a field connected to MBSR (e.g. education, psychology, medicine) or demonstration of equivalent understanding through work experience in a related field.

Delivery of treatment: We will assess participants' perceptions of provider warmth and credibility using brief measures based on the validated Working Alliance Inventory,⁵³ and Therapist Empathy Scale⁵⁴ at Weeks 4 and 8 of the intervention. Feedback will be provided to the interventionist.

Receipt of treatment and enactment of treatment skills: Adherence to the prescribed MBQR practices will be monitored through class attendance, practice logs and diaries. Adherence data will be collected weekly during the course of the intervention.

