Fidelity Monitoring: Intervention fidelity will be ensured by (1) rigorous, program specific training for the instructor with feedback (2) recording of all sessions with a 10% quality audit reviewed with instructor after each cohort (3) monitoring participant attendance, home practice of treatment skills, and understanding of skills (see Feasibility) (4) a comprehensive mixed methods approach (e.g. practice logs) for understanding of treatment enactment. In assessing MBQR Instructor competency and treatment fidelity, a randomly selected 10% or more of the recorded sessions will be reviewed by trained research assistants and rated for proportion of adherence to the MBQR curriculum guide. Intervention integrity for MBQR will be assessed using the Mindfulness-Based Interventions-Teaching Assessment Criteria (MBC-TAC), which is the most respected quantitative approach world-wide for assessing mindfulness-based programs. In order for the MBQR intervention and its associated data to be included in the sample, the instructor needs to demonstrate 90% or greater curriculum adherence.

Protocol Deviations:

Protocol deviations will be reported to the Brown University IRB. A description of the deviations, and any effects on the protection of human subjects will be documented. Investigator(s) will review protocol deviations and determine on a case by case base which data (if any) will be excluded from the final data set.

Participant Rights and Confidentiality

Institutional Review Board

The protocol, the informed consent document, and any subsequent modifications, will be reviewed and approved by the Brown University IRB responsible for oversight of the study.

Informed Consent Documents

Prior to enrollment, all participants will be provided with an IRB-approved Informed Consent document. The consent form will describe the purpose of the study, the procedures to be followed, and the risks and benefits of participation. Informed consent is an ongoing process. Participants will first be presented with the Informed Consent Form (ICF) at the time of initial online screening. They will have the option to download and save the ICF and will also be prompted to click through the ICF text in full (displayed on multiple screens in Qualtrics). The consent process will continue into the Zoom Interviews #1 and #2, where a trained research staff member will review the ICF with the participant and answer any questions they might have.

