Mindfulness-based Queer Resilience (MBQR) to Promote Mental and Sexual Health among Sexual and Gender Minority Young Adults: Statistical Analysis Plan

A mixed-methods approach will be used to understand feasibility and acceptability of this randomized controlled trial. Descriptive statistics will be used to summarize feasibility and acceptability measures from the full sample. These measures include recruitment rates, retention/attrition rates, session attendance, Client Satisfaction Questionnaire, and session evaluation form.

In addition, qualitative data from exit interviews will be analyzed using template analysis, a thematic analysis methodology that applies data reduction techniques for rapid turnaround, often used in intervention development and refinement research.

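### Data can be excluded for protocol deviations at the investigators' discretion, with no criteria, no deadline and no masking, and the SAP does not define its analysis sample

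*Protocol*

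**What the plan says.** Protocol section 6, Protocol Deviations, sends deviations to the IRB and adds: "A description of the deviations, and any effects on the protection of human subjects will be documented". On exclusion, the investigators are to "determine on a case by case base which data (if any) will be excluded from the final data set". Nothing further is said about grounds, timing or who else takes part.

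The paragraph before it, Fidelity Monitoring, holds a separate exclusion that applies to the MBQR arm only and turns on how closely the instructor adheres to the curriculum: "In order for the MBQR intervention and its associated data to be included in the sample, the instructor needs to demonstrate 90% or greater curriculum".

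The other relevant statements are:

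- Protocol section 2 gives the size: "total Aim 3 sample size = up to 60 participants enrolled and randomized", with up to 30 per arm. It also says the trial is meant to assess MBQR's effect on the listed outcomes.
- Protocol section 6, Withdrawal during intervention, says of people who stop either course that "they will still be invited to take part in the follow up assessments".
- The SAP, first paragraph, says: "Descriptive statistics will be used to summarize feasibility and acceptability measures from the full sample". The measures are recruitment, retention, session attendance, a satisfaction questionnaire and a session evaluation form.

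**The concern.** An exclusion rule is safe when its grounds are fixed in advance, or when the person applying it cannot see arm or outcome. This rule has neither protection. A reader of the results could not tell whether a record left the data set for a reason that would have applied equally in the other arm, or with a different result.

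Two things are at stake. The first is the set of feasibility and acceptability figures, which are the SAP's whole quantitative output. If those removed tend to have poor retention or attendance, the intervention looks more feasible than it was. The second is any comparison of the arms on HIV/STI testing or sexual risk, which section 1 of the protocol names as primary outcomes. Removing randomised people selectively undoes the balance that randomisation gave. With at most 30 per arm, a few exclusions are enough to matter.

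**Working it through.** The plan gives no power, error rate or expected rate, so there is no figure of its own to reproduce. The check has two parts.

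**1. Does anything limit the discretion?**

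| Possible limit | What the documents give |
|---|---|
| Criteria for exclusion | None; 'deviation' is not defined |
| Decision before outcomes are seen | Not required; under Data Management, data are downloaded routinely while collection is under way |
| Masking of the decision-makers | None described. The arms are live Zoom classes and self-paced modules (sections 2 and 5). Provider Training says of the MBQR instructors: "Training will be delivered by PI". The PI also reviews participant progress with staff (Frequency of Monitoring) |
| Limit on the PI's access to identifiers | Present under Participant Confidentiality, but it covers personal identity, not allocation |
| IRB reporting | Leaves a record of deviations; gives the IRB no stated role in data exclusion |
| Follow-up of those who stop the course | Protects data collection, not inclusion in the analysis |
| The SAP's 'full sample' | Undefined; no intention-to-treat statement or analysis set in either document |

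Nothing in the list closes the gap.

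**2. How far could a few exclusions move a figure?**

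Inputs: n = 30 per arm (protocol sections 1 and 2). Assumed: k = 3 people removed (10% of an arm), all with the unfavourable result, and the starting counts x below. The documents supply none of these assumed values.

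Shift in a rate = x/(n − k) − x/n = xk / [n(n − k)]. With n = 30 and k = 3 this is 3x/810 = x/270.

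| Assumed x of 30 | Before | After (x/27) | Shift, points |
|---|---|---|---|
| 15 | 50.0% | 55.6% | 5.6 |
| 18 | 60.0% | 66.7% | 6.7 |
| 21 | 70.0% | 77.8% | 7.8 |
| 24 | 80.0% | 88.9% | 8.9 |

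At a lower starting rate the shift is smaller: 9/30 = 30.0% becomes 9/27 = 33.3%, or 3.3 points.

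Mean sessions: if 27 people average 8 of 10 and three average 1, the mean is (27 × 8 + 3 × 1)/30 = 219/30 = 7.3. Without the three it is 8.0.

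Between arms, with 15/30 in each and no true difference: removing three unfavourable MBQR participants gives 55.6% against 50.0%, a gap of 5.6 points. Also removing three favourable controls gives 15/27 = 55.6% against 12/27 = 44.4%, a gap of 11.1 points. For a normally distributed outcome with no true effect, removing the worst 3 of 30 in one arm shifted the difference by about 0.19 SD (50,000 simulated trials).

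**The neighbouring rule.** If one MBQR cohort of 8 to 10 people (section 4) failed the 90% adherence criterion and its data were dropped, MBQR would fall from 30 to between 30 − 10 = 20 and 30 − 8 = 22, while control stayed at 30. The protocol does not say whether adherence is judged by cohort, so this too is an assumption. It shows why the two rules need to be reconciled together.

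**The case against.** The case on the other side limits the point in several ways, and most of it stands.

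- **Deviation may not mean non-adherence.** A reader might infer that missed sessions, late surveys or untaken tests would be treated as deviations and removed. The documents do not say so. They treat deviations as IRB-reportable events. They handle attendance and practice as adherence data, expect dropout, make homework optional and pay only for components completed. The term is undefined, so that reading is not ruled out, but it cannot be called likely.
- **Excluding data is not excluding people.** Discarding a badly collected nail sample leaves the retention denominator at 30. The figures above assume that whole participants are removed.
- **Knowledge of allocation is inferred.** A reader might take it as stated that investigators know the arm and always decide after randomisation. Neither is written. The lack of masking is a strong inference from the visible difference between arms and the PI's training role. Screening or consent deviations can precede randomisation.
- **There is no conflict with the withdrawal rule.** Inviting people to follow-up and later reviewing data can coexist. The plain reading of 'full sample' is everyone, although nothing in the SAP secures that reading.
- **The SAP plans no between-arm test.** To say the rule breaks the planned randomised comparison goes too far. HIV/STI testing is not among the measures that the SAP summarises.

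The objection does not supply a limit on the discretion. IRB reporting leaves an audit trail, which is useful, but it does not govern which data are analysed.

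**Conclusion.** The point holds in this form: the protocol states an open, discretionary exclusion rule, and nothing in either document constrains it. Exclusion with knowledge of arm or outcome is possible. It could distort the feasibility summaries and any between-arm estimate that is reported.

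The size is a worst case, not an expectation. It is about 6 to 9 points on a rate that starts between 50% and 80%, and 11.1 points between arms if selection acts in both. It rests on 30 per arm, three whole participants removed, all with the unfavourable result, and assumed starting rates. Exclusion of single measurements, or exclusion unrelated to outcome, would do less.

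A reader might infer that selective exclusion occurred or was intended. The documents do not support that; they show only that it could not be ruled out afterwards. Because the SAP is descriptive and plans no test between arms, this is something that should be fixed, not a fault that invalidates the plan.

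**What to change.** Replace the exclusion sentence under Protocol Deviations with:

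> All randomised participants are kept in the arm assigned and in the denominators for retention, attendance and outcomes, whatever their protocol deviations. Only individual measurements that are technically invalid under criteria fixed before outcome data are reviewed (for example, an unusable nail sample) are set to missing. Deviations and any excluded measurements are listed by type, arm and reason. Any analysis omitting deviators is a labelled sensitivity analysis.

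In the SAP, define 'full sample' as all randomised participants for post-randomisation measures. Recruitment rates need their own, earlier denominator.

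Reconcile this with the 90% adherence sentence under Fidelity Monitoring by making that exclusion a labelled sensitivity analysis as well. Otherwise the two paragraphs would contradict each other.

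An outright ban on excluding any data would be the wrong remedy, because it would keep invalid measurements in the main summaries.

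The cost is one protocol paragraph, one amended sentence on fidelity, one SAP sentence and a short list of technical validity criteria. The downside is that the feasibility figures may look slightly less favourable.

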Mindfulness-based Queer Resilience (MBQR) to Promote Mental and Sexual Health among Sexual and Gender Minority Young Adults: Statistical Analysis Plan

A mixed-methods approach will be used to understand feasibility and acceptability of this randomized controlled trial. Descriptive statistics will be used to summarize feasibility and acceptability measures from the full sample. These measures include recruitment rates, retention/attrition rates, session attendance, Client Satisfaction Questionnaire, and session evaluation form.

In addition, qualitative data from exit interviews will be analyzed using template analysis, a thematic analysis methodology that applies data reduction techniques for rapid turnaround, often used in intervention development and refinement research.

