Participants who were randomized to the control group will be offered a MBQR-hybrid course after the 6-month follow-up assessment is complete. This additional course is optional. Control group members who opt to take MBQR-hybrid will be invited to complete a post-intervention assessment and exit interview. The total length of involvement for control group participants who opt not to take MBQR-hybrid will be around 6-months from the time of enrollment to the time of the final research assessment, while control group participants opting into the MBQR-hybrid will be done with participation in the study around 9-12 months after enrollment. Participants randomized to the MBQR intervention group will be invited to complete a 1-year follow up assessment in addition to the other assessments, thus their involvement in the study will last around 12 months from the time of enrollment. The study interventions last 10 weeks and take place in the first two months of study involvement.

The figure below provides a visual outline of the study flow, including the screening and assessment sequence.

3. Selection Criteria for Aim 3:

The following is the most updated inclusion/exclusion criteria:

- Inclusion criteria:
 - (1) assigned male at birth,
 - (2) being 18 to 34 of age,
 - (3) identify as a cisgender man or nonbinary,
 - (4) reside in the United States,
 - (5) can read and speak English,
 - (6) engaged in condomless anal sex with another man in past 6 months,
 - (7) endorse distress, measured by the PHQ-9 and GAD-7,
 - (8) possess a device (phone, tablet, computer) that allows for online conferencing.
 - (9) HIV-negative at time of screening
- About HIV status: HIV status will be assessed in 2 steps: (1) by self-report in online survey and (2) by rapid HIV testing via Zoom with a trained study RA (optional; other options could include local testing or by self-report). We will provide rapid oral HIV testing in Aim 3. At screening, participants will participate in rapid oral HIV testing (optional), and at post-intervention and follow-up, participants will engage in both HIV and STI testing (see more in HIV/STI testing protocol).
- Exclusion criteria: YMSM will be excluded from the study if they are determined to have symptoms that would prevent them from giving meaningful consent or participate in study activities including any of the following criteria:
 - (1) Significant cognitive impairment
 - (2) Psychosis
 - (3) Imminent suicidal risk

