4. Steps in Recruitment, Screening, and Assessment:

Recruitment Timeline and Procedures

- 1) Timeline for recruitment:
 - a. Recruitment efforts will commence 2-4 months prior to the start of each study intervention.
 - b. Enrollment for each round will end on the date of the run-in session. Any individuals screened for the study after that date will be deferred to the next round (if applicable).
 - c. All preparatory efforts to be ready at least 8 weeks prior to the RCT
 - d. Participants will be recruited and enrolled into cohorts based on intervention scheduling. We anticipate enrolling around 8-10 participants

into each intervention and control group (e.g., we anticipate running two summer cohorts and one fall cohort).

- 2) Multi-Pronged Recruitment Strategy: Recruitment will be conducted primarily through four methods:
 - a. Community Advisory Board (CAB) member social networks – IRB approved recruitment materials will be provided to CAB members to distribute to their social networks and for them to post on their social media accounts.
 - b. Online social media (e.g., Facebook-based community groups for gay and bisexual men, Reddit threads, Twitter, etc.)
 - c. Emails to University/College campus groups, Community-based Organizations, and partner health groups (e.g., the Fenway Institute in Boston)
 - d. Targeted recruitment through BuildClinical® - see separate BuildClinical® recruitment proposal

Screening Procedures: Participants will be screened for eligibility in three steps.

- 1) Online Screening Form - First, individuals interested in the study, will be prompted to complete a brief (5-15 minute) internet-based screening form via Qualtrics to determine their initial eligibility. Individuals who screen eligible will then be redirected to a separate Qualtrics form where they can review the Informed Consent Form (ICF) and complete a contact form for follow-up.

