Baseline Procedures, Enrollment, Run-In, and Randomization

- 1) Baseline Procedures:
 - a. Eligible participants will be asked to complete a baseline survey via Qualtrics that is estimated to take 60-80 minutes to complete (see separate Assessment document for details).
 - b. At baseline they will also be mailed a Cortisol genetic testing kit that will provide them with the necessary equipment to collect a baseline nail sample (see separate cortisol nail sampling protocol for details). Participants will then mail back the completed sample back to the study staff for further processing. Participants will be compensated \$20 for each genetic sample provided.
 - c. Following baseline survey completion, participants are considered as "enrolled and ready to be randomized".
- 2) Run-in Session: Prior to randomization participants will be asked to attend a mandatory 30-minute introduction session via Zoom that will serve as a 'run-in' session for individuals interested in the study. The purpose of this session will be to:
 - a. Provide a brief overview of the randomization process and intervention arms. This includes an emphasis on the time commitment required for the interventions and for the study as a whole.
 - b. Introduce the research team and the course interventionists.

- c. Walk through the HIV/STI self testing and genetic cortisol sampling procedures; remind participants to mail in their samples / submit their results.
- d. Answer any questions.
- e. Allow participants an opportunity to opt out of the study (submitted privately by email, phone, text, etc.) prior to the randomization. Note that participants can withdraw at any time. The run-in session allows participants an additional opportunity to opt out prior to being included in the randomization. This helps with overall group balance and retention.
- f. Participants who complete the baseline assessment and opt in to the study following the run-in session will be included in the randomization; they will be coded as “enrolled and randomized”.

3) Randomization:

- a. Prior to intervention commencement, participants will be randomly assigned to one of two groups: (1) MBQR Intervention group; or (2) a health education control group.
- b. Control group participants who complete the study will be given the opportunity to participate in the intervention (MBQR-hybrid) after the 6-month follow up assessments are completed.

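### The SAP analyses none of the protocol's declared primary or secondary outcomes and specifies no comparison of MBQR with control

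*SAP*

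**What the plan says.** Protocol section 1 (Specific Aims, Aim 3) opens by setting out to examine feasibility and acceptability, then declares outcomes of a different kind:

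- Two outcomes are put first: "Primary outcomes are HIV and STI testing and self-reported sexual risk behaviors"
- Four further domains rank below these: "Secondary outcomes are stress biomarker (fingernail cortisol levels), psychological health, minority stress and coping"
- Feasibility measures follow, with neither label attached to them: "The study will examine recruitment and retention, number of sessions attended, self-reported at-home practice of mindfulness, completion of assessment, and acceptability of the intervention"

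Section 2 (Aim 3 Study Design Overview) describes a two-arm trial against a health education control, up to 30 per arm, and adds: "The study is intended to evaluate the impacts of MBQR on the outcomes outlined in the Specific Aims above". Both arms are assessed post-intervention and at 6 months. The 1-year assessment is for the intervention arm only.

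The SAP is two short paragraphs. On quantitative data it says: "Descriptive statistics will be used to summarize feasibility and acceptability measures from the full sample". It lists recruitment, retention or attrition, attendance, a satisfaction questionnaire and a session evaluation form. The rest concerns template analysis of exit interviews.

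Two protocol rules bear on who would be analysed. Under Fidelity Monitoring, MBQR data enter the sample only if the instructor reaches at least 90% curriculum adherence. Under Protocol Deviations, investigators may exclude data case by case. The SAP mentions neither.

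**The concern.** The protocol promises an evaluation of impact on named primary outcomes, and the SAP contains no analysis that could deliver it. Two consequences follow.

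First, everything that determines a result for the primary outcomes remains open until the data are in hand: definition, time point, population, estimate and handling of missing data. The definition matters particularly for testing. Both arms are mailed kits after the intervention and at 6 months and are paid per completed test. Completed testing, testing frequency and test result are therefore three different outcomes, and so is testing with or without the study kits counted.

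Second, the adherence rule names MBQR data only and acts after randomisation. If it excluded participants, it would do so in one arm, and the remaining comparison would no longer be the one that was randomised.

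**Working it through.** **Outcomes against the SAP**

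| Declared outcome | Status in protocol | Analysis in SAP |
|---|---|---|
| HIV and STI testing | primary | none |
| Sexual risk behaviour | primary | none |
| Nail cortisol | secondary | none |
| Psychological health | secondary | none |
| Minority stress | secondary | none |
| Coping | secondary | none |

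The count is 6 of 6 without an analysis (5 of 5 if minority stress and coping are read as one domain). The protocol has no statistical section that fills the gap; Data Management says only that data are exported for analysis. The documents give no planned effect size, power or precision to reproduce.

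**Data already scheduled through 6 months, 60 participants**

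- Surveys at baseline, post-intervention and 6 months: 60 × 3 = 180. Nail samples: 60 × 3 = 180.
- HIV/STI testing occasions post-intervention and at 6 months: 60 × 2 = 120. Section 3 states that "at post-intervention and follow-up, participants will engage in both HIV and STI testing".
- Weekly assessments covering condomless sex, PHQ-9 and GAD-7: up to 60 × 10 = 600.

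**Precision of a between-arm estimate**

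*Mean difference*, 95% half-width in SD units = t × √(1/n₁ + 1/n₂):

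- 30 v 30: 2.002 × 0.2582 = 0.517
- 24 v 24 (20% loss assumed): 2.013 × 0.2887 = 0.581
- 20 v 30 (one MBQR group of 10 excluded, assumed): 2.011 × 0.2887 = 0.580

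*Baseline-adjusted*, with three binary balancing factors (60 − 6 = 54 df): 0.518 × √(1 − r²) = 0.494, 0.448 and 0.370 at assumed baseline correlations r of 0.3, 0.5 and 0.7.

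*Testing uptake* (Newcombe interval for a risk difference): 15/30 v 15/30 gives ±0.238; 24/30 v 24/30 gives ±0.202.

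*Grouping.* MBQR is taught in groups and the control course is self-paced. Section 4 says "we anticipate running two summer cohorts and one fall cohort", so about three MBQR groups of 10. SE = √((1 + 9 × ICC)/30 + 1/30).

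| Assumed ICC | Half-width, 58 df | Satterthwaite df | Half-width, Satterthwaite df |
|---|---|---|---|
| 0.01 | 0.528 | 6.9 | 0.625 |
| 0.05 | 0.572 | 5.5 | 0.714 |
| 0.10 | 0.622 | 4.6 | 0.822 |

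**Why the testing denominator must be stated**

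The documents give no retention or uptake rate, so these are assumptions. Let uptake u among those retained be equal in both arms. If no recorded test counts as not tested, the difference is u × (MBQR retention − control retention):

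| Retention, MBQR v control | u = 50% | u = 80% |
|---|---|---|
| 80% v 90% | 0.5 × (−0.10) = −5 points | 0.8 × (−0.10) = −8 points |
| 70% v 90% | 0.5 × (−0.20) = −10 points | 0.8 × (−0.20) = −16 points |

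The observed-data difference is 0 in every cell. If retention were lower in the control arm, the signs would reverse.

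**The case against.** The best defence is that this is a 60-person pilot whose Aim 3 begins with feasibility and acceptability. A descriptive SAP suits that aim, and no efficacy test is needed. That is right as far as it goes, and it is why one of the two repairs is simply to relabel the protocol. It does not remove the contradiction: the protocol itself calls the behavioural outcomes primary, randomises against an active control and states an intent to evaluate impact.

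Several narrower objections stand in part.

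- Definitions may exist in documents not available here. The baseline section says "see separate Assessment document for details", and a separate HIV/STI testing protocol is also cited. The weekly assessments name condomless sex, PHQ-9 and GAD-7. That narrows the definition gap but supplies no scoring rule or analysis.
- People who leave the MBQR course or stop the control course are still invited to follow-up (section 6, Withdrawal), and the SAP refers to the full sample. Both favour keeping randomised participants, but neither overrides the adherence rule. The unit that rule excludes is not stated, so 20 v 30 is a scenario.
- The retention, uptake, correlation and ICC values are illustrations. The finding does not depend on them.
- Taking all randomised as the lead denominator for testing is a choice, which is why the observed-data version is needed beside it.

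**Conclusion.** The concern holds and should be resolved before outcome data are analysed. No declared primary or secondary outcome has a stated analysis, and no MBQR-versus-control estimate is specified, so the SAP as written cannot answer the protocol's impact question. This rests on the two documents' text alone.

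The intervals assume two-sided 95% confidence and, at 30 per arm, complete data. They show that this sample supports exploratory estimates and not efficacy claims. Losing one MBQR group of 10 would widen the mean-difference interval only from ±0.52 to ±0.58 SD; the greater harm is that the loss falls in one arm. Under the assumed retention differences, the choice of denominator alone moves the testing result by 5 to 16 points.

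**What to change.** Reconcile Specific Aims and the Study Design Overview with the SAP by one of two routes.

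**Route A: add the analysis to the SAP.**

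1. Define each declared outcome. For testing: completed testing, frequency or result, and whether study-kit tests count. The compensation note on tests outside the study kit is attached to baseline HIV testing only, so it does not settle this for follow-up. For sexual risk: scoring, recall period and whether the weekly reports are used.
2. Give by-arm summaries and the MBQR-minus-control estimate with 95% CI at post-intervention and 6 months, labelled exploratory with no efficacy claim.
3. Include all randomised participants in their assigned arm. Amend Fidelity Monitoring and Protocol Deviations so that those exclusions are sensitivity analyses only.
4. Adjust continuous outcomes for baseline where collected and, as numbers allow, for the factors balanced at randomisation.
5. If testing uptake is the outcome, report a risk difference with all randomised as denominator (no recorded test = not tested) and an observed-data sensitivity analysis. For other outcomes, report numbers missing by arm and state the missing-data rule.
6. State the grouping of MBQR participants as a limitation.

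**Route B: relabel the protocol.** Make feasibility and acceptability primary, label the other outcomes exploratory and remove the sentence on evaluating impact. This alone leaves the exclusion rules in place and the exploratory outcomes without an analysis, so say how they will be summarised and in whom.

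**Under either route**, report retention and assessment completion by arm through 6 months beside the overall figures, and satisfaction by arm if controls complete the form. A pooled rate cannot show MBQR's own feasibility. Attendance and mindfulness home practice apply to MBQR only.

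**Cost.** Route A needs SAP and protocol wording and modest analysis of data already scheduled; its downside is wide intervals. Route B is mainly wording. Protocol changes under either route need written IRB approval (Reporting Plan).
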